Add one more oral: Metform, Sulfonylureas, or TZD (i.e. Actos)		Intensify basal, or add bolus		If not on DPP-4, add DPP-4 or start GLP-1 and decrease SU. If already on DPP-4, then discontinue DPP-4, add GLP-1 and decrease SU		Add GLP-1, decrease SU If already on DPP-4, then discontinue DPP-4, add GLP-1, and decrease SU. Self-directed basal insulin titration (3-0-3 scheme) until visit 2	
 FV 2 (3 month visit)							
HbA1c >7.5%	HbA1c <=7.5	HbA1c >7.5	HbA1c <=7.5	HbA1c >7.5%	HbA1c <=7.5	HbA1c >7.5	HbA1c <=7.5
Add basal or oral(s) if not at max	Continue regimen	Intensify Basal/Bolus	Continue regimen	Add basal	Continue regimen	Basal/Bolus Continue GLP-1	Continue regimen
 FV3 (6 month visit)							
Obtain final HbA1c and other outcomes							

b. Study duration and number of study visits required of research participants.

The study duration is 6 months.

c. Blinding, including justification for blinding or not blinding the trial, if applicable.

Upon confirmation of study eligibility, signed informed consent form, and the baseline data collection, 30 participants will be randomized in a 1:1 ratio to one of the two groups.

Randomization will be in variable blocks (2 and 4) after stratification by age (65 to 74; vs 75 and older), using the Moses-Oxford algorithm, adapted for SAS statistical software. The randomization scheme will be generated by the Statistician and the Study Coordinator will convey actual randomization assignment to participants. Trial participants will know their intervention assignments, as will intervention physicians. However, study staff involved in follow-up data collection will be kept masked to participants' randomization assignments.

Date: June 11, 2013

Principal Investigator: [name]

Application Number: NA_00052707

d. Justification of why participants will not receive routine care or will have current therapy stopped.

N/A. Patients will receive routine diabetes care

e. Justification for inclusion of a placebo or non-treatment group.

Not applicable.

f. Definition of treatment failure or participant removal criteria.

Participants can be removed from study by [name], the leader of clinical intervention at any time without patient consent for any of the following reasons: (1) if the participant fails to follow directions for participation in the study; (2) if a specific FDA-approved diabetes regimen appears harmful to participant; or (3) if the study is cancelled.

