g. Description of what happens to participants receiving therapy when study ends or if a participant's participation in the study ends prematurely.

Participants will remain under the care of their personal physician both during the study and after the study ends.

5. Inclusion/Exclusion Criteria

Patient inclusion criteria:

- Type 2 diabetics diagnosed for at least 6 months
- Patients ages \geq 65 years and older
- Active patients in the Bay West Endocrinology practice
- Inadequately controlled on oral agents and/or basal insulin with HbA1c between 8.0% and 12%
- Eligible for randomization to either treatment group
- Patients willing to follow either treatment arm including regimen using one or more injectables
- Patients to have an English Reading Level of Grade 6 or above
- Patients residing at home

Patient exclusion criteria:

- Unwilling to use a regimen that may contain using one or more injections
- Using short acting insulin prior to the study
- Using GLP-1 in past 10 weeks
- History of hypoglycemia unawareness or episodes needing emergency intervention
- End-stage renal disease
- Dementia
- Blindness
- Terminal illness

Date: June 11, 2013

Principal Investigator: [name]

Application Number: NA_00052707

- Judged by investigators as unlikely to follow protocol because of known non-compliance, psychiatric disease, alcohol or drug abuse.

6. Drugs/ Substances/ Devices

- The rationale for choosing the drug and dose or for choosing the device to be used.

The study objective is to compare the effectiveness of two diabetes treatment strategies (regimen using FDA approved traditional diabetes drugs only vs. regimen including incretin-based classes of FDA approved diabetes medication) in elderly patients with type 2 diabetes. All of these diabetes drugs are FDA approved for standard use.

- Justification and safety information if FDA approved drugs will be administered for non-FDA approved indications or if doses or routes of administration or participant populations are changed.

This study will use FDA approved drugs for diabetes treatment.

- Justification and safety information if non-FDA approved drugs without an IND will be administered.

Not applicable.

7. Study Statistics

- Primary outcome variable.

Time to achieve glycemic target (HbA1c <7.5%). This goal will be defined as HbA1c measures at follow-up visits.

- Secondary outcome variables.

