All serious adverse events will be documented in patient's study chart, collected as part of study procedures and also reported to Medical Monitor; however, only those that meet the criteria that are serious, unexpected, and associated with the FDA-approved study medications will be reported to both JHU/GBMC IRBs within 10 working days. If in doubt about whether or not the event meets the criteria of serious, unexpected and associated with the FDA-approved diabetes medications, it will be up to the JHU Principal Investigator to make the final determination after consulting with at least 1 of the study's sub-investigators.

Safety Monitoring Plan

There will be no formal Data and Safety Monitoring Board (DSMB) for this pilot trial using FDA-approved medications in the manner that they were approved for the patient population that FDA approved. Patients will remain under their own physicians' care. [name] at Johns Hopkins, will serve as Medical Monitor for the study and for serious and unexpected adverse events. As stated in section 8c. of this protocol, all serious adverse events will be documented in patient's study chart, collected as part of study procedures, and also be reported to Medical Monitor Principal Investigator. All other AEs will be logged and submitted to the IRB at Continuing Review.

d. Legal risks such as the risks that would be associated with breach of confidentiality.

The investigative team and MODEL are keenly aware of the need to protect participant confidentiality, as well as corresponding legal requirements, including those mandated by HIPAA (Health Insurance Portability and Accountability Act). All data collected and stored electronically will be password protected and saved in a secured fashion. All study related computers will be under firewall protection and will maintain automated virus update mechanisms. Timely notification regarding relevant patches will be provided. Hard copy of the data collection forms will be stored in locked cabinets or areas. Only authorized personnel will have access to these locked areas. In addition, all study staff annually sign a confidentiality statement attesting to their understanding of, and willingness to abide by, the staff written policies on research ethics and confidentiality. Access to the data entry system is password protected and restricted to personnel trained to use the system.

e. Financial risks to the participants.

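### Section 4f removes participants from the study for reasons that may relate to outcome, with no outcome assessment afterwards and no analysis as randomised

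*Combined protocol and SAP*

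**What the plan says.** Section 4f opens with "Participants can be removed from study by" the clinician who leads the intervention, "at any time without patient consent for any of the following reasons". The first two reasons are "1) if the participant fails to follow directions for participation in the study; (2) if a specific FDA-approved diabetes regimen appears harmful to participant". The remaining one, "3) if the study is cancelled", is administrative and plays no part here. What ends is participation in the study, not just use of a regimen.

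Section 4g, which covers premature end of participation, offers one sentence: "Participants will remain under the care of their personal physician both during the study and after the study ends". It does not mention outcome assessment.

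On masking, section 4c states: "Trial participants will know their intervention assignments, as will intervention physicians". Staff who collect follow-up data are masked.

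The primary outcome in section 7 is the time until HbA1c falls below 7.5%, and "This goal will be defined as HbA1c measures at follow-up visits". Table 1 in section 4a places HbA1c at randomisation, month 3 and month 6. The statistical plan in section 7 names no analysis population, between-arm method or handling of removals. On safety data, section 8c has serious events documented and reported to the Medical Monitor, and adds: "All other AEs will be logged and submitted to the IRB at Continuing Review".

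**The concern.** Stopping a regimen and leaving the trial are different events, and section 4f provides only for the second. Three features make the resulting loss potentially selective.

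- **Related to outcome.** Apparent harm overlaps the secondary outcomes of hypoglycemia, weight and adverse events. Failure to follow directions may go with poorer glycemic control.
- **Related to arm.** The arms use different drugs, and injectable incretins belong to one arm only. The abstract itself hypothesises that hypoglycemia, weight gain and side effects differ between arms.
- **Made with knowledge of the arm.** The person who decides is presumably unmasked, since intervention physicians know the assignment. Masked data collectors cannot prevent a selective removal.

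At stake are the comparison of the two strategies, which is the stated objective in section 2, and the parameters that section 7 wants for a confirmatory trial. Removals by arm and reason are themselves useful planning data, and the plan does not ask for them.

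**Working it through.** **Inputs from the protocol.** 30 participants randomised 1:1, so 15 per arm (section 4c); HbA1c after baseline at months 3 and 6 only (Table 1); confidence level 95% (section 7).

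**Inputs assumed.** The protocol gives no removal or attainment rate. Let *f* be the share of a given outcome group lost to removal, from 10% to 40%. True attainment at 6 months is 50%. For the primary outcome, 25% reach target at month 3, a further 25% at month 6, and 50% never.

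**The plan's own figures.** Section 7 gives only half-widths for single estimates and none for a difference or for losses. Its ±15.5 points for a 50% proportion at N = 30 is not reproduced: 1.96 × √(0.25/30) = 17.9 points. That is a separate matter and is not used below.

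**What is lost, by timing of removal**
- Before month 3: no primary outcome data.
- Between months 3 and 6: no final HbA1c. A participant already at target at month 3 keeps a complete primary outcome; one not at target is left undetermined.
- Outcomes collected before removal, and adverse events already documented or logged, remain.

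**Percent at target at 6 months**
- A. Non-attainers lost from one arm: 0.5 / (0.5 + 0.5(1 − f)) − 0.5
- B. Attainers lost from one arm: 0.5(1 − f) / (0.5(1 − f) + 0.5) − 0.5
- C. Same *f* of non-attainers lost in both arms, true rates 50% and 70%: change from the true difference of 20 points

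**Primary outcome.** Removal after month 3, one arm, Kaplan-Meier attainment by month 6 against a true 0.50. Kaplan-Meier is my choice, because section 7 names no method.
- D. Never-attainers lost: 1 − 0.75 × (1 − 0.25 / (0.25 + 0.5(1 − f)))
- E. Month-6 attainers lost: 1 − 0.75 × (1 − 0.25(1 − f) / (0.25(1 − f) + 0.5))

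| Case | f = 0.1 | f = 0.2 | f = 0.4 |
|---|---|---|---|
| Patients lost in A (7.5 × f) | 0.75 | 1.5 | 3 |
| A, points | +2.6 | +5.6 | +12.5 |
| B, points | −2.6 | −5.6 | −12.5 |
| C, points | −0.5 | −1.1 | −3.0 |
| D, attainment (shift in points) | 0.518 (+1.8) | 0.538 (+3.8) | 0.591 (+9.1) |
| E, attainment (shift in points) | 0.483 (−1.7) | 0.464 (−3.6) | 0.423 (−7.7) |

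If both arms have a true 50% and lose the same share of non-attainers, the bias in the difference is 0.

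**In whole patients.** With 8 of 15 at target (53.3%), removing 1, 2 or 3 non-attainers gives 8/14 = 57.1%, 8/13 = 61.5% or 8/12 = 66.7%. These are shifts of +3.8, +8.2 and +13.3 points.

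**Bounds.** Each missing participant widens that arm's best-to-worst-case range by 1/15 = 6.7 points.

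**Scale.** The standard error of a difference between two arms of 15 at 50% is √(2 × 0.25/15) = 18.3 points, so the 95% half-width is 1.96 × 18.3 = 35.8 points. The shifts in A run from 2.6/18.3 = 0.14 to 12.5/18.3 = 0.68 standard errors.

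**Planning SD, extreme case only.** If removal took exactly the worst 10% of a normal outcome, the SD would fall to 0.844 of its true value. A sample size proportional to SD² would then be understated by 1 − 0.844² = 29%. The conclusion does not rest on this.

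**The case against.** The strongest case against is about size. All removal rates are assumed. The top of the range needs 3 of 15 removed from one arm, every one a non-attainer, and nobody from the other. A bias of 0.14 standard errors leaves the coverage of a 95% interval almost unchanged, and even 0.68 lowers it only to about 90%.

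The protocol also makes removal less likely than the upper range implies. The wording in 4f is permissive. Section 5 excludes people judged unlikely to follow the protocol. Section 4a foresees stopping a baseline drug for an adverse event without saying that the participant leaves, and both arms are multi-drug strategies. Section 7 specifies no formal between-arm analysis, so the missing statement on analysis as randomised is partly one symptom of a thin analysis plan. The consent form was not available for this review and might set terms for follow-up after removal.

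Most of this stands as a limit on magnitude. It does not close the gap. Comparison is the stated objective even though no method is given. The request in section 4a to attend through month 6 is not said to continue after removal from the study. A confidence interval does not reveal bias of this kind. Whatever the consent form says, section 7 still lacks an analysis set.

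**Conclusion.** The concern holds. Followed as written, section 4f with section 4g and the HbA1c schedule loses outcomes for reasons that may depend on response, tolerability and arm, and nothing in the protocol text recovers them or fixes the analysis to the randomised groups. Under the assumed rates and one-arm loss, the bias at 6 months is between 2.6 and 12.5 points in either direction. For the primary outcome it is between +1.8 and +9.1 points or between −1.7 and −7.7, depending on who is lost. It vanishes when losses and true rates are equal across arms. Actual direction and size cannot be known in advance. For a pilot with a half-width near 36 points this is a modest bias. It should be corrected because the remedy is cheap and outcomes not collected at the time cannot be fully recovered later.

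**What to change.** Leave the clinical decisions in section 4f unchanged and add:

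1. In 4f or 4g: a participant removed under reason (1) or (2) is still asked to attend the 3- and 6-month outcome assessments (HbA1c, weight, hypoglycemia, adverse events and questionnaires) unless consent is withdrawn.
2. In section 7: all participants are analysed in the arm to which they were randomised.
3. In section 7: removals are reported by arm, reason and month.

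The cost is two or three sentences in an amendment, plus a few more retained visits and their payments. Section 10 implies $80/4 = $20 per visit, so at most $40 for someone removed before month 3. All participants are active patients of one practice, so the visits are obtainable from those willing to come. Recovery will be incomplete: some people removed under reason (1) may not attend in any case.

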Secondary Outcomes: a) Percent achieving glycemic target at 6 month; b) Overall hypoglycemia measured by glucose meter; c) Total cholesterol, HDL cholesterol, and triglyceride; d) Fasting glucose insulin, and fructosamine; e) blood pressure (BP) and heart rate determined by the OMRON 907-XL; f) Weight, height, and waist circumference; g) EQ-5D Questionnaire; h) Diabetes Quality of Life Questionnaire¹⁴; i) Diabetes distress¹⁵ (2 screener questions); j) self-care; k) incontinence¹⁶ (1 question).

Other Data: a) Demographics: tobacco use, health insurance status, education level, and live alone status; b) Medication history including monitoring adherence, which will be self-reported for each of the prescribed medications for glycemic control.

Adverse Events: Hypoglycemic episodes requiring assistance by medical/paramedical personnel, overnight hospitalization, diabetes-related deaths, and other outcomes that the Medical Monitor deems important.

- Statistical plan including sample size justification and interim data analysis.

Date: June 11, 2013

Principal Investigator: [name]

Application Number: NA_00052707

One of the purposes of this pilot trial is to collect needed parameters for future planning of a larger scale confirmatory RCT. To this end, the frequency distribution of parameters of interested will be collected and described at baseline and over follow-up. Repeated measures over follow-up will provide estimate for intra-individual correlations that will be needed in sample size/power determination for the future trial. Repeated measures of HbA1c will also allow examination of HbA1c trajectory over time to inform the feasibility of interpolate the time to reaching HbA1c target threshold based on fixed interval assessments.

Using width of 95% CI as a measure of precision in parameter estimation, a sample size of 30 will provide estimation precision of $\pm 0.31 \times \text{SD}$ for a continuous variable, $\pm 15.5\%$ for a binary proportion of 50%, and $\pm 9.3\%$ for a binary proportion of 10%. For subgroup estimation with $N = 15$ per group, the above precision will be inflated by 1.4.

d. Early stopping rules.

Formal stopping rules are not planned for this pilot trial.

8. Risks

a. Medical risks, listing all procedures, their major and minor risks and expected frequency.

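### The only assistance-based hypoglycemia event requires professional help, so episodes a participant could not self-treat but a lay person treated are not counted as such

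*Combined protocol and SAP*

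**What the plan says.** The Adverse Events paragraph in Section 7 names "Hypoglycemic episodes requiring assistance by medical/paramedical personnel, overnight hospitalization, diabetes-related deaths", and the sentence ends "and other outcomes that the Medical Monitor deems important". No other event in the plan is defined by the need for help during hypoglycemia. The secondary outcomes in the same section include "b) Overall hypoglycemia measured by glucose meter", with no glucose threshold, severity grade or testing frequency.

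Section 8 adds two general routes. For serious events: "All serious adverse events will be documented in patient's study chart, collected as part of study procedures"; these also go to the Medical Monitor. For the rest: "All other AEs will be logged and submitted to the IRB at Continuing Review". Seriousness follows the FDA description, which the protocol does not reproduce.

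On the population, Section 5 requires "Patients residing at home" and age 65 or over, and excludes "History of hypoglycemia unawareness or episodes needing emergency intervention". The Other Data paragraph in Section 7 collects "tobacco use, health insurance status, education level, and live alone status". Randomization (Section 4c) is stratified by age only.

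Table 1 (Section 4a) has no row for hypoglycemia, meter readings or adverse events. For the calls at 1.5 and 4.5 months it lists only medication use, with a note that they are check-ins.

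**The concern.** The event turns on who gave the help, not on whether the participant could self-treat. Take the same incapacitating episode in two participants. One lives with a spouse who treats it, and it is not counted. The other lives alone, an ambulance is called, and it is counted. The plan expects living arrangements to vary, since it records them.

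This matters for three reasons. The abstract hypothesizes less hypoglycemia with the incretin-based regimen. The background cites severe episodes as a clinical concern in older patients. Adverse events are a secondary outcome (Section 4a), and the pilot is meant to supply parameters for a larger trial (Section 7). A rate limited to professional assistance would enter that planning as if it described all episodes needing help.

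**Working it through.** **Where a lay-assisted episode could be recorded**

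- Assistance-based event (Section 7): not counted, because the help was not professional.
- Meter outcome (Section 7, item b): recorded if someone took a reading. The participant may be unable to test during the episode; a helper could, or the participant could on recovery. Nothing marks the reading as an assisted episode.
- Medical Monitor clause (Section 7): possible, but discretionary and without a stated criterion.
- Serious-event route (Section 8): possible if the FDA description is met. No field for who assisted is described.
- General log (Section 8): possible, again without a stated severity grade or helper field.
- Table 1: no scheduled question that would bring the episode to light.

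The episode can be on record, but no route identifies it as one that the participant could not self-treat.

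**Size**

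The plan states no hypoglycemia rate or expected count, so there is no figure of its own to reproduce.

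Inputs from the documents: 30 participants, 1:1 allocation, 6 months. Follow-up is 30 × 0.5 = 15 patient-years, or 7.5 per arm, if all complete.

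Assumed inputs: r = 0.1 to 0.3 episodes per patient-year needing anyone's help; f = 10% to 50% of these attended by medical or paramedical personnel.

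Poisson model: expected count as written = r × 15 × f; with any helper = r × 15; P(none) = exp(−expected count).

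| Case | Expected, as written | P(none) | Expected, any helper | P(none) |
|---|---|---|---|---|
| r = 0.1, f = 10% | 0.15 | 86% | 1.5 | 22% |
| r = 0.2, f = 25% | 0.75 | 47% | 3.0 | 5% |
| r = 0.3, f = 50% | 2.25 | 11% | 4.5 | 1% |

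For one arm at the middle values, the expected counts are 0.2 × 7.5 × 0.25 = 0.375 and 0.2 × 7.5 = 1.5, so P(none) is 69% and 22%.

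The recorded rate is f times the rate of episodes needing help. Under the assumed f, it is too low by a factor of 1/0.5 = 2 to 1/0.1 = 10.

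**When would zero be the likelier result?** With a 6-month risk p per participant of a professionally assisted episode, P(none in 30) = (1 − p)^30. This exceeds one half only if p < 1 − 0.5^(1/30) = 2.3%. The documents do not say which side of that value the true risk lies.

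**What a zero would show.** The one-sided 95% upper limit after 0 of 30 is 1 − 0.05^(1/30) = 9.5%. A zero count would not show that the risk is absent, even for the event as defined.

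**The case against.** The strongest reply is that the plan has other routes. The adverse-event list is open-ended, all other adverse events are logged, serious events go to the Medical Monitor, and participants are seen or called five times after randomization. The outcome that matches the hypothesis is overall hypoglycemia by meter, which does not depend on who helps. This stands against one inference a reader might draw, that lay-treated episodes vanish from the trial. They need not. What is missing is a classification and a scheduled question.

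A reader might also infer that severe hypoglycemia will probably appear absent. The documents give no rate to support that, and at the middle assumed values zero has a 47% chance, so at least one counted event is slightly more likely. The protocol does not call this event severe hypoglycemia, nor call hypoglycemia its main risk. A low count could also come from the small sample or from the exclusion of prior unawareness and emergency episodes, which may reduce lay-assisted episodes too.

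A third inference would be that household composition biases the comparison. Randomization balances it in expectation. With about 15 per arm, chance imbalance is possible and can be described from the live-alone variable.

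Finally, professionally attended episodes are easier to verify, and participants know their assignment, so lay-assisted reports are more open to reporting bias. That is a fair reason to keep the narrow count, though not to make it the only one. It is also true that the broader definition would yield only 1.5 to 4.5 expected events over both arms, too few to compare regimens. Its value here is a better planning rate.

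**Conclusion.** The concern holds in a limited form. The one hypoglycemia event defined by need for help leaves out help from lay people, in a home-dwelling population aged 65 or over, and no other route in the plan identifies those episodes as assisted. The likely effect is undercounting that depends partly on household composition and carries into planning of the larger trial. It is not a demonstrated bias between arms.

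Over the assumed range, the chance of recording none is about 11% to 86% as written against 1% to 22% with any helper counted. These figures rest on assumed rates and attended fractions, full 6-month follow-up and independent episodes. Clustering of episodes within participants would raise the chance of zero under both definitions. The direction does not depend on the assumptions: the broader definition captures at least as many episodes. This is a worthwhile, inexpensive improvement to a descriptive pilot, not a flaw that undermines it.

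**What to change.** In the Adverse Events paragraph of Section 7, count hypoglycemic episodes in which the participant needed the help of any other person to treat the episode. Record who helped: household member, other lay person, paramedic, or clinic or hospital staff. Report medically or paramedically attended episodes as a subset, which preserves the current count. Add a row to Table 1 so that such episodes are asked about at the existing follow-up visits and at both calls.

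The cost is one sentence in the protocol, one field on the event form and one question per contact, with no extra visits. The downside is that lay-assisted episodes are less verifiable and, with assignment known to participants, open to reporting bias. Showing the professionally attended subset beside the total lets the reader judge that.

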As type 2 diabetes progresses in older persons, intensification is often required to achieve adequate glycemic control but with increased risk of adverse effects as a result of age related changes in drug metabolism. Incretin-based classes of medication, for example incretins, improve glycemic control in older persons. Some clinical evidence suggested that certain DPP-4 inhibitors (e.g. vildagliptin and sitagliptin) are particularly suitable for frail and elderly patients because less gastrointestinal effects than metformin and α - glucosidase inhibitors, and have a low risk of the hypoglycaemic events¹¹. The American Association of Clinical Endocrinologists (AACE) and American College of Endocrinology (ACE) Consensus Statement¹² recently included incretin-based classes of drugs in the Diabetes Algorithm for Glycemic Control. However, the recommendation is largely based on expert opinions, not head-to-head comparisons. A recent federally-sponsored literature synthesis by our group² pointed out the deficiencies of evidence in evaluating newest agents and two-drug combinations. Most important, evidence supporting one regimen over the other for elders is lacking. In this pilot trial, we will test real-world, practice-based strategies comparing traditional treatment to treatment including incretin-based drug classes in reducing glycemia safely in diabetic elders in the short run (3-6 months).

4. Study Procedures

- a. Study design, including the sequence and timing of study procedures (distinguish research procedures from those that are part of routine care).

Design Overview: This study will be a single center, randomized controlled trial (RCT) with 2 parallel arms. The participants will be 30 adults age 65 or older with type 2 diabetes mellitus. After informed consent and screening, these elderly adults will be randomly assigned to one of two anti-diabetic regimens (both regimens use only FDA-approved medications):

- 1) a regimen with traditional drugs only (e.g. insulin, metformin, sulfonylureas, TZDs); or
- 2) a regimen including incretin-based drugs (e.g. GLP-1 analogues and receptor agonists, DPP-4 inhibitors, amylin analogues).

The primary outcome variable is time to achieve glycemic target (HbA1c <7.5%). Secondary outcomes are overall hypoglycemia, weight, diabetes quality of life, and adverse events.

Date: June 11, 2013

Principal Investigator: [name]

Application Number: NA_00052707

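### The precision figures given as 95% confidence intervals for N = 30 are too narrow: correct 95% half-widths are about 15% wider with z and about 20% wider with t

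*Combined protocol and SAP*

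**What the plan says.** The statistical plan in Section 7 (Study Statistics) contains no power calculation. It justifies the sample size by precision alone, in a sentence that begins "Using width of 95% CI as a measure of precision in parameter estimation, a sample size of 30 will provide estimation precision of". Three half-widths are then listed: for a continuous measure, ±0.31 SD; when the true proportion is 50%, ±15.5 percentage points; and when it is 10%, ±9.3 points. For estimates within one group of 15, it says that "the above precision will be inflated by 1.4".

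The plan does not say which interval method was used, and it mentions neither a 90% level nor a one-sided limit.

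The sample size is 30 wherever it appears: in the Abstract, in the Design Overview of Section 4a ("The participants will be 30 adults age 65 or older with type 2 diabetes mellitus"), under Recruitment, in Section 4c ("30 participants will be randomized in a 1:1 ratio to one of the two groups") and in Section 7.

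**The concern.** The usual 95% half-width for a mean at N = 30 is 1.96/√30 = 0.36 SD. A stated value of 0.31 SD is therefore too small on sight, and both proportions look short by the same ratio.

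This matters because Section 7 gives the collection of parameters for planning a larger confirmatory trial as one purpose of the pilot. A reader would conclude that 30 patients deliver a precision that they do not. The per-group figures inherit the shortfall. Binary outcomes are directly affected: the percentage at glycemic target at 6 months is a listed secondary outcome.

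**Working it through.** **Inputs (all from Section 7).** Two-sided 95% confidence; N = 30; 15 per group; factor 1.4 for the per-group figures; stated half-widths 0.31 SD, 0.155 and 0.093.

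**Formula.** Half-width = c × SD/√N, with SD = √(p(1 − p)) for a proportion (0.5 at 50%, 0.3 at 10%).

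**Step 1: the multiplier behind the plan's figures.**
- Mean: 0.31 × √30 = 1.698
- 50%: 0.155/√(0.25/30) = 1.698
- 10%: 0.093/√(0.09/30) = 1.698

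The three figures agree with one another, so a misread digit is not the explanation. The 95% multipliers are 1.960 (z) and 2.045 (t, 29 df). A multiplier of 1.698 corresponds to 91.0% confidence on z, or 90.0% on t with 29 df.

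**Step 2: half-widths at N = 30.**

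| Basis | Mean (SD) | At 50% (points) | At 10% (points) | Ratio to plan |
|---|---|---|---|---|
| Plan | 0.31 | 15.5 | 9.3 | 1 |
| 95%, z | 0.358 | 17.9 | 10.7 | 1.154 |
| 95%, t (29 df) | 0.373 | 18.7 | 11.2 | 1.204 |
| 90%, z | 0.300 | 15.0 | 9.0 | 0.969 |
| 90%, t (29 df) | 0.310 | 15.5 | 9.3 | 1.001 |

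**Step 3: could another 95% method for proportions give the plan's figures?** Half-widths for 15/30 and 3/30:
- Wilson: 16.8 and 11.1 points
- Jeffreys: 17.2 and 10.7 points
- Clopper-Pearson: 18.7 and 12.2 points

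Even a Wald interval cut off at zero gives 10.4 points at 10%. All exceed 15.5 and 9.3. Reading the stated precision as full width only enlarges the gap.

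**Step 4: possible sources.** Two calculations reproduce all three figures after rounding:
- 90% t at N = 30: 0.3102, 15.51, 9.31
- 95% z at N = 40: 0.3099, 15.49, 9.30

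The number needed for 0.31 SD is (1.96/0.31)² = 39.97, about 40 by z; by t it is 42 to 43. The documents never mention 40, and they do not show which slip occurred.

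**Step 5: 15 per group.**
- Plan: 1.4 × (0.31, 15.5, 9.3) = 0.434 SD, 21.7 points, 13.0 points
- 95% z: 0.506 SD, 25.3 points, 15.2 points (ratio 1.166)
- 95% t (14 df) for a mean: 0.554 SD (ratio 1.276)

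The factor 1.4 is itself sound under z (√2 = 1.414). With t at both sizes the ratio is 0.554/0.373, about 1.48.

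**Step 6: the 10% case as an interval.** The plan implies 10 ± 9.3, that is 0.7% to 19.3%. Like for like, the 95% Wald interval is 10 ± 10.7, or −0.7% to 20.7%. The 95% Wilson interval for 3/30 is 3.5% to 25.6%. At 15 per group the Wald lower limit is 10 − 15.2 = −5.2%, and the plan's own figures already give 10 − 13.0 = −3.0%.

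**The case against.** The strongest case on the other side accepts the arithmetic and disputes its weight and the details.

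- **Label rather than calculation.** The 0.95 quantile of t on 29 df reproduces all three figures. It is the distance to a one-sided 95% limit, so the numbers might be kept and relabelled as 90% intervals. As an account of the cause this is plausible, but the ± notation attached to a 95% CI means two-sided. Relabelling would also leave the per-group statement inexact: 90% t at N = 15 gives 0.455 SD, 22.7 and 13.6 points, a factor of about 1.47 rather than 1.4.
- **The gap depends on the method.** This stands. With Wilson at 50% the shortfall is only 9% at N = 30 (16.8 against 15.5), and 4% at N = 15 (22.6 against 21.7). The 15% and 20% figures hold for the z and t forms.
- **Wald against Wilson at 10%.** This also stands. Most of the move in the upper limit from 19.3% to 25.6% comes from Wilson's asymmetry; correcting the multiplier alone moves it to 20.7%.
- **Little depends on it.** This is a pilot with a fixed N, no power claim and no formal stopping rule, and a later trial would use the observed estimates with their own intervals. That limits the consequence. It does not make the sentence correct, and no other justification for the sample size is offered.

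**Conclusion.** The concern holds. Read as written (two-sided 95%, N = 30), the stated precision is too narrow. The correct half-widths are 15% wider by z and 20% wider by t, and no standard 95% method for a proportion comes down to the stated values. At 15 per group the z-based values are 17% wider than the plan implies, and a t-based mean is 28% wider.

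The result assumes only simple random sampling and full data on all 30 participants. Any dropout would widen the intervals further. The cause cannot be settled from the documents. The point should be corrected, but it does not call the design or the planned analyses into question.

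**What to change.** Keep N = 30, recompute at 95%, and name the method. Suggested text:

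*With N = 30, the two-sided 95% CI half-width is ±0.37 SD for a mean (t distribution) and ±17.9 percentage points for a proportion of 50% (normal approximation); for a proportion of 10% the 95% Wilson interval is 3.5% to 25.6%. With N = 15 per group, the half-widths are ±0.55 SD and ±25.3 points, and the Wilson interval for 10% is 2.3% to 34.0%.*

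If a single normal multiplier is preferred throughout, the values for a mean are ±0.36 SD and ±0.51 SD, and the factor 1.4 may stay. I would use t for means because z gives a noticeably narrower figure at 15 per group (0.51 against 0.55 SD).

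Wilson is advised at 10% because the Wald lower limit is below zero at both sizes. The N = 15 Wilson interval is a planning value only, since 10% of 15 is 1.5 events; the neighbouring observable results are 1/15 (1.2% to 29.8%) and 2/15 (3.7% to 37.9%).

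As an optional addition, the plan could give the 95% half-width for the difference between groups of 15. By z this is 1.96 × √(2/15) = ±0.72 SD for a mean, and 1.96 × √(0.5/15) = ±36 points at 50%.

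The cost is wording only, with no extra patients, visits or data. The stated precision becomes less favourable.
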